3.1.1 Design/Schema

3.2 DRUG ADMINISTRATION

LB-100 will be infused over 2 hours (+/- 15 minutes) via IV infusion. The dose established from a Phase I study will be 2.33 mg/m². At the end of infusion, each subject will have an EKG (within 30 minutes of the end of infusion).

Abbreviated Title: Phase II Study LB100 gliomas

Version Date: 06/02/2022

3.3 FOLLOW-UP

All patients will be evaluated in person 1-3 days following craniotomy and followed for at least 30 days after infusion of LB-100 for toxicity assessment. During the first week after infusion with LB-100, renal function tests and liver function tests will be performed. Two to 3 weeks following discharge from the hospital, all patients will return to the clinic or be seen by their local physician for a physical exam and bloodwork. Given that the methodologies utilized are similar across all laboratories, no significant variability is expected and there is no anticipation that study data will be affected. Patients will be contacted by phone (or seen in clinic) at approximately 30 days post craniotomy and will be asked a non-leading question to determine whether any new AEs have occurred and to follow up on any ongoing AEs.

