3.4 STUDY CALENDAR

STUDIES TO BE OBTAINED	PRE-TREATMENT	AT CRANIOTOMY	3 DAY FOLLOW UP (+/- 2 Days)	2-3 WEEK FOLLOW UP	30 DAY FOLLOW- UP
Informed Consent	X				
Medical History	X				
Physical Examination	X			X	
Tumor Imaging -MRI (preferred) or CT scan	X				
Documentation of tumor diagnosis	X				
Laboratory Evaluation ¹	X		X	X	
24 hour Creatinine clearance (if required per section 2.1.1.6)	X				
12-lead EKG	X	X ⁵			
LB100	X				
PK/PD ^{2,3}	X	X			

STUDIES TO BE OBTAINED	PRE-TREATMENT	AT CRANIOTOMY	3 DAY FOLLOW UP (+/- 2 Days)	2-3 WEEK FOLLOW UP	30 DAY FOLLOW- UP
Adverse Events Notation		X	X	X	X ⁴

Pre-treatment studies should be performed within 28 days of receiving study drug.

¹ Laboratory Evaluation: CBC, differential, platelets, PT, PTT, INR, total protein, albumin, calcium, phosphorus, magnesium, glucose, BUN, creatinine, sodium, potassium, uric acid, total bilirubin, alkaline phosphatase, LDH, ALT, AST. The pregnancy test for women of child bearing age will be done at screening only.

² Plasma PK: see section [5.1.1.1](#)

³ Tissue PK: see section [5.1.1.2](#)

⁴ Follow- up: see section [3.3](#)

⁵EKG within 30 minutes of the end of infusion.

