6 DATA COLLECTION AND EVALUATION

6.1 DATA COLLECTION

The PI will be responsible for overseeing entry of data into a 21 CFR Part 11-compliant data capture system provided by the NCI CCR and ensuring data accuracy, consistency and timeliness. The principal investigator, associate investigators/research nurses and/or a contracted data manager will assist with the data management efforts. Primary and final analyzed data will have identifiers so that research data can be attributed to an individual human subject participant.

All adverse events, including clinically significant abnormal findings on laboratory evaluations, regardless of severity, will be followed until return to baseline or stabilization of event.

Document adverse events from the first study intervention, Study Day 1 through Study Day 30 (safety visit). Beyond 30 days after the last intervention, only adverse events which are serious and related to the study intervention need to be recorded.

For patients whose pathological evaluation at craniotomy demonstrates treatment effect (e.g. necrosis or inflammation as a result of therapy) rather than tumor recurrence, adverse events will still be monitored from the first study intervention, Study Day 1 through Study Day 30 (safety visit).

Grade 1 events need not be captured, collected, or reported.

An abnormal laboratory value will be recorded in the database as an AE **only** if the laboratory abnormality is characterized by any of the following:

- Results in discontinuation from the study
- Is associated with clinical signs or symptoms
- Requires treatment or any other therapeutic intervention
- Is associated with death or another serious adverse event, including hospitalization.
- Is judged by the Investigator to be of significant clinical impact
- If any abnormal laboratory result is considered clinically significant, the investigator will provide details about the action taken with respect to the test drug and about the patient's outcome.

End of study procedures: Data will be stored according to HHS, FDA regulations and NIH Intramural Records Retention Schedule as applicable.

Abbreviated Title: Phase II Study LB100 gliomas

Version Date: 06/02/2022

Loss or destruction of data: Should we become aware that a major breach in our plan to protect subject confidentiality and trial data has occurred, this will be reported expeditiously per requirements in section **7.2.1**.

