The following macroscopic pathology findings were reported in the 1.25 mg/kg/day group: test article-related pale kidneys in males at the primary necropsy, as well as test article-related higher kidneys weights in males and females. At the recovery necropsy, kidney weights remained higher in 1.25 mg/kg/day group males.

Evaluation of microscopic pathology revealed adverse, test article-related nephrosis of the kidneys in the 0.75 and 1.25 mg/kg/day group males and females, which persisted or progressed in the males at the recovery necropsy. Minimal to severe nephrosis was observed in the kidney and was characterized by tubular degeneration and regeneration in the cortex and/or medulla. Minimal to mild nephrosis was most often observed in the medulla and/or occasionally the cortex. The 0.75 and 1.25 mg/kg/day group males had minimal to mild dilatation of the renal pelvis. The nephrosis correlated to pale kidneys in the males; higher kidney weights in the 1.25 mg/kg/day group males and females; higher serum urea nitrogen, phosphorous, and creatinine levels, and higher incidence of urine occult blood, protein, and leukocytes in the 1.25 mg/kg/day group males and/or females. Moderate nephrosis in the cortex and medulla persisted in the 0.75 and 1.25 mg/kg/day males and was accompanied by moderate interstitial fibrosis at the recovery necropsy and was associated with higher kidney weights in the 1.25 mg/kg/day group males at the recovery necropsy. Neither nephrosis nor interstitial fibrosis was observed in the females at the recovery necropsy.

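### The last scheduled labs are timed from hospital discharge and full AE recording from dosing, so after a long stay those labs can fall where only serious, related events need be recorded

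*Combined protocol and SAP*

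**What the plan says.** Three sections bear on the point.

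- **Section 3.3 (Follow-up).** The last scheduled visit with laboratory tests, which also includes an examination, is counted from discharge: "Two to 3 weeks following discharge from the hospital, all patients will return to the clinic or be seen by their local physician". An earlier sentence adds: "During the first week after infusion with LB-100, renal function tests and liver function tests will be performed". Toxicity follow-up is to last a minimum of 30 days from the infusion. A contact about 30 days after craniotomy, by phone or in clinic, asks about AEs.
- **Section 3.4 (Study Calendar).** The visit is headed "2-3 WEEK FOLLOW UP", with no statement of what the weeks are counted from, and stands before the 30-day column. The row "Laboratory Evaluation ¹" is marked before treatment, at the 3-day visit (window of 2 days either way) and at the 2-3 week visit, but not at 30 days. The row "Adverse Events Notation" is marked at craniotomy and at all three follow-up contacts.
- **Section 6.1 (Data Collection).** All AEs above Grade 1 are documented from the first study intervention, Study Day 1, through Study Day 30. Then: "Beyond 30 days after the last intervention, only adverse events which are serious and related to the study intervention need to be recorded". A laboratory abnormality counts as an AE only if it meets one of a short list of conditions.

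**The concern.** The calendar's column order assumes that the last labs come before the 30-day contact and inside full AE recording. Section 3.3 does not guarantee this, because its clock starts at discharge and has no upper limit in days from dosing.

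After a long enough stay, the only laboratory panel scheduled beyond the first week falls where a non-serious or unrelated finding need not be recorded. The 30-day contact has no labs and may be a phone call, so it would not detect a silent creatinine change.

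Renal function is the natural example. Reduced creatinine clearance was the dose-limiting toxicity in the phase I study (section 1.2.4). In the repeat-dose rat study, nephrosis "persisted or progressed in the males at the recovery necropsy" (section 14.1.2). The drug had not been given to patients with glioma before (section 12.4.1.1), and at most 25 patients will be enrolled, so a single unrecorded event would be a visible share of the safety data.

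**Working it through.** The plan gives no figure to reproduce here. The check is day arithmetic.

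**Inputs**
- First study intervention (infusion) = Study Day 1 (6.1). Surgery follows the infusion by 2 to 4 hours (3.1), so dosing and craniotomy fall on about the same day.
- Last scheduled labs: 14 to 21 days after discharge (3.3).
- Full AE recording: through Study Day 30 (6.1).
- Discharge on Study Day D. The documents give no length of stay, so D is varied.

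**Formula.** The visit falls on Day D+14 to D+21.
- It can fall after Day 30 when D+21 > 30, that is, D of 10 or more.
- It must fall after Day 30 when D+14 > 30, that is, D of 17 or more.

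| Discharge day | Visit window | Relative to Day 30 |
|---|---|---|
| 4 | 18-25 | wholly inside |
| 9 | 23-30 | wholly inside |
| 10 | 24-31 | partly outside |
| 16 | 30-37 | partly outside |
| 17 | 31-38 | wholly outside |

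**Sensitivity to day counting.** Section 6.1 also describes the limit as 30 days after the last intervention. Read as elapsed days, the last day is Study Day 31. The conditions become D+21 > 31 and D+14 > 31, so the thresholds move to Day 11 and Day 18.

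**Interval without required renal or liver tests, discharge on Day 10**
- The 3-day visit is Study Day 1+3 = 4. With 2 days either way, its draw is on Day 2 to 6.
- Section 3.3 also asks for renal and liver tests within a week of infusion, so the last such test could be as late as Day 1+7 = 8.
- The next required draw is on Day 24 to 31.
- Shortest interval: 24 - 8 = 16 days. Longest: 31 - 2 = 29 days.

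The interval is therefore about 16-29 days, depending on draw days. It lengthens by one day for each further day in hospital. These are protocol-required tests only; routine inpatient tests are not counted.

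**The case against.** The case against is substantial, and most of it stands as a limit on size.

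- **A reader might infer that AE recording closes at Day 30.** It does not. Serious, related events must still be recorded, and the 30 days in 3.3 are a minimum. The calendar also marks AE notation at the visit itself. That mark does not say which rule governs a visit held after Day 30, so the inconsistency remains.
- **A reader might infer that data are lost selectively in the patients most likely to have toxicity.** The documents do not support this. They give neither length of stay nor reasons for long stays. An AE that prolongs hospitalization is itself serious (8.1.2) and is followed to resolution (8.2). Patients are monitored after surgery (12.4.1.1), AEs already recorded are followed until they settle (6.1), and the 30-day contact runs from craniotomy whatever the discharge date.
- **A reader might infer that the 3-day visit is the only earlier source of labs.** Section 3.3 separately requires renal and liver tests in the first week; the interval above allows for this.
- **A reader might infer from the animal data that late-onset renal injury is to be expected.** Those findings followed repeated daily dosing, whereas this trial gives one dose, and nephrosis was already present at the primary necropsy. In humans, the dose-limiting toxicity was reversible and occurred at 3.1 mg/m²; 2.33 mg/m² was tolerated with no rise in creatinine.

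What survives is narrow: a new abnormality, above Grade 1, meeting the laboratory-AE conditions in 6.1, not both serious and related, and first seen at a visit after Day 30. None of the safeguards requires that event to be recorded.

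**Conclusion.** The point holds as a mismatch between two clocks. It rests on infusion being Study Day 1, on the 2-3 week visit being counted from discharge as 3.3 states, and on the absence of any cap, which a reading of 3.3, 3.4 and 6.1 confirms. The thresholds carry an uncertainty of one day from the two ways 6.1 expresses its limit.

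How many patients would be affected cannot be estimated. If all are discharged by Day 9, none are. Safety is not a listed objective, and the PK endpoint, the two-stage rule and the sample size are untouched. The severity is minor; the point is worth making because it is cheap to close.

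**What to change.** 1. Reconcile sections 3.3, 3.4 and 6.1 so that the last scheduled labs always fall within full AE recording. The sponsor should choose the anchor for the visit and state it in both 3.3 and the calendar column.
2. As a data-collection rule, state in 6.1 that all AEs are recorded through the later of Study Day 30 and completion of the 2-3 week follow-up visit. This closes the gap whichever anchor is chosen. The sentence should also say that Study Day 30 applies if the visit does not take place.

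The cost is a sentence or so in each place. No visit or test is added. The only downside is a few more days of AE recording for patients with long stays.

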3.4 STUDY CALENDAR

STUDIES TO BE OBTAINED	PRE-TREATMENT	AT CRANIOTOMY	3 DAY FOLLOW UP (+/- 2 Days)	2-3 WEEK FOLLOW UP	30 DAY FOLLOW- UP
Informed Consent	X				
Medical History	X				
Physical Examination	X			X	
Tumor Imaging -MRI (preferred) or CT scan	X				
Documentation of tumor diagnosis	X				
Laboratory Evaluation ¹	X		X	X	
24 hour Creatinine clearance (if required per section 2.1.1.6)	X				
12-lead EKG	X	X ⁵			
LB100	X				
PK/PD ^{2,3}	X	X			

STUDIES TO BE OBTAINED	PRE-TREATMENT	AT CRANIOTOMY	3 DAY FOLLOW UP (+/- 2 Days)	2-3 WEEK FOLLOW UP	30 DAY FOLLOW- UP
Adverse Events Notation		X	X	X	X ⁴

Pre-treatment studies should be performed within 28 days of receiving study drug.

¹ Laboratory Evaluation: CBC, differential, platelets, PT, PTT, INR, total protein, albumin, calcium, phosphorus, magnesium, glucose, BUN, creatinine, sodium, potassium, uric acid, total bilirubin, alkaline phosphatase, LDH, ALT, AST. The pregnancy test for women of child bearing age will be done at screening only.

² Plasma PK: see section [5.1.1.1](#)

³ Tissue PK: see section [5.1.1.2](#)

⁴ Follow- up: see section [3.3](#)

⁵EKG within 30 minutes of the end of infusion.

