2.1.2 Exclusion Criteria

- 2.1.2.1 Patients who are receiving any other investigational agents.
- 2.1.2.2 Uncontrolled intercurrent illness including, but not limited to, ongoing or active infection, symptomatic congestive heart failure, unstable angina pectoris, cardiac

arrhythmia, or psychiatric illness/social situations that would limit compliance with study requirements.

- 2.1.2.3 Patients unwilling to undergo craniotomy.
- 2.1.2.4 Pregnant women are excluded from this study because the safety of PP2A inhibition on a developing fetus has not been established. Because there is an unknown but potential risk for adverse events in nursing infants secondary to treatment of the mother with LB100, breastfeeding should be discontinued if the mother is treated with LB100.
- 2.1.2.5 Patients may not have had prior chemotherapy or biologic therapy in the 4 weeks prior to study entry. For patients who have been treated with targeted therapy, 5 half-lives of that therapy (or 28 days, whichever is shorter) must have passed prior to enrollment in the study.
- 2.1.2.6 Known HIV-positive patients on combination antiretroviral therapy are ineligible because of the potential for pharmacokinetic interactions with LB100. Appropriate studies will be undertaken in patients receiving combination antiretroviral therapy when indicated.
- 2.1.2.7 Patients who are receiving strong CYP450 inducers or inhibitors are ineligible

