2.2.2 Screening activities performed after a consent for screening has been signed

The following activities will be performed only after the subject has signed the study consent OR the consent for study 01-C-0129 (provided the procedure is permitted on that study) on which screening activities may also be performed. Assessments performed at outside facilities or on another NIH protocol within the timeframes below may also be used to determine eligibility once a patient has signed the consent.

Within 28 days prior to receiving study drug the following assessments are required:

- A complete history and neurological examination (to include documentation of the patients' Karnofsky Performance Status).
- Neuro-imaging confirming tumor progression shall be performed on all patients. MRI is preferred over CT scan.
- 12-lead EKG
- Laboratory Evaluation:
 - CBC with differential, platelets, PT, PTT, INR
 - Total protein, albumin, calcium, phosphorus, magnesium, glucose, BUN, creatinine, sodium, potassium, alkaline phosphatase, ALT, AST, total bilirubin, direct bilirubin), LDH and uric acid
 - 24-hour urine collection for Creatinine Clearance (if required per section **2.1.1.6**)
 - Urine or serum β-HCG

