2.4 BASELINE EVALUATION

All baseline evaluation procedures should be done prior to the study treatments. They do not need to be repeated if performed within 28 days prior to study drug initiation.

- A complete history and physical (including baseline blood pressure measurement) and neurological examination (include documentation of the patients' height, weight, and Karnofsky Performance Status).
- A baseline standard NOB Gd-DPTA enhanced MRI should be performed.

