3.7.1 Criteria for removal from protocol therapy

- Completion of protocol therapy, craniotomy, PK and PD evaluations.
- Unacceptable Toxicity
- Investigator discretion
- Positive Pregnancy Test

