4 CONCOMITANT MEDICATIONS/MEASURES

All participating subjects will undergo a craniotomy for resection of recurrent tumor.

Concomitant medications/measures as clinically indicated will be delivered. The surgical team will provide routine care as needed. Participation in this study will not limit any routine care.

Only those medications that the patient is taking at baseline on a routine basis or medications that cause an AE will be captured in database. Thus one time medications and PRN medications will not be captured in database except those used to treat adverse events.]

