16.2 PK WORKSHEET

Cover Letter Form

PKs to [name]

Page: [name]

Samples must be retrieved and processed within 30 minutes.

PLEASE clearly label the PIVs for PK's/LB-100 infusion, respectively.

Protocol # 17-C-0037, Drug: LB-100

Cycle 1 Day 1 LB-100 Dose: _____

Staff Obtaining Samples: _____ (printed name)

Signature/initials: _____

When documenting in CRIS, please include the details in your note:

- Pre-chilled 6 ml Sodium Heparin tube
- Date and time sample obtained
- If the collection time differs from the "scanned time," please indicate this in your note with actual time sample obtained.
- If sample or EKG is obtained outside of the protocol-defined time window (+/- 15 min), please indicate reason

Abbreviated Title: Phase II Study LB100 gliomas

Version Date: 06/02/2022

- Update Research Nurse via phone or email if sample outside of the defined window.

DATE: _____	Protocol # DRUG - LB-100									
PKs to [name] Page: [name]						Clock Used: _____				
Part 1 Cycle 1 Day 1		LB-100 Dose: _____	m/Ht: _____	Wt: _____	BSA: _____	Research Nurse: _____ name phone beeper PI: [name]				

You may draw PK's through a CVC; or, through a peripheral line (please note location of blood draw under "Comments") ** You must populate each "scheduled time cell" (after the Pre-infusion cell) using the EOI as reference as soon as EOI is determined. Two RNs must independently check your scheduled time column.
										
DO NOT DRAW PK'S THROUGH THE SAME LINE AS DRUG ADMINISTRATION.										
Study Day	Time Interval	Amount/Type/Tube// Handling	Test	Sched Time (Military)	Actual Time (Military)	Special Instructions	Comments	Signature	Reason if missed	Documented in CRIS Serial Testing Note (initial)
LB-100 Infusion Start Time: _____ LB-100 Infusion End Time: _____										
Day 1	pre LB-100	One 6 mL Sodium Heparin (Green Top) Date and time tube	PK			Page [name] - [name] Lab Place on wet ice and refrigerate				
	End of Infusion (2hr post infusion start)	One 6 mL Sodium Heparin (Green Top) Date and time tube	PK			Page [name] - [name] Lab Place on wet ice and refrigerate				
	End of Infusion (2hr post infusion start)	N/A	EKG			Please provide the EKG to the Research Nurse				
	30 min post EOI	One 6 mL Sodium Heparin (Green Top) Date and time tube	PK			Page [name] - [name] Lab Place on wet ice and refrigerate				
	1hr post EOI	One 6 mL Sodium Heparin (Green Top) Date and time tube	PK			Page [name] - [name] Lab Place on wet ice and refrigerate				

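### The only required pregnancy test may be up to 28 days old when the single LB100 dose is given

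*Combined protocol and SAP*

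**What the plan says.** - **Exclusion.** Section 2.1.2.4: "Pregnant women are excluded from this study because the safety of PP2A inhibition on a developing fetus has not been established". Section 2.1.1.9 adds that effects on the fetus are unknown, requires contraception from before entry and throughout participation, and tells a woman who suspects pregnancy to inform her physician at once.
- **Test and window.** Urine or serum beta-HCG is on the screening list in section 2.2.2, introduced by "Within 28 days prior to receiving study drug the following assessments are required". The Study Calendar (3.4) gives the same limit: "Pre-treatment studies should be performed within 28 days of receiving study drug". Its footnote 1 states: "The pregnancy test for women of child bearing age will be done at screening only".
- **Baseline.** Section 2.4 lists no pregnancy test and says of baseline procedures: "They do not need to be repeated if performed within 28 days prior to study drug initiation".
- **Dosing day.** Section 3.2 describes the infusion and an EKG at its end. In the worksheet (16.2) the pre-dose row asks for "One 6 mL Sodium Heparin (Green Top) Date and time tube" and nothing else.
- **After a positive result.** Section 3.7.1 lists "Positive Pregnancy Test" as a reason for removal from therapy. Section 8.5.1 deals with a pregnancy once it is known.
- **Exposure.** Section 14.1.5 specifies one dose. Section 3.1 places the infusion 2 to 4 hours before surgery in patients admitted for that operation. Section 12.4.2 says participants gain no direct benefit.

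**The concern.** The exclusion protects a fetus only if it is verified close to the exposure. Here the verification may be four weeks old at the time of the only dose. After screening, the remaining safeguards either lower the chance of conception (contraception) or rely on someone already knowing or suspecting that the patient is pregnant (the reporting duty, the removal criterion, section 8.5.1). None of them finds a pregnancy that nobody suspects. Because the drug is given once, stopping treatment when a pregnancy comes to light later cannot undo the exposure. What is at stake is an avoidable fetal exposure of unknown consequence in a study that offers the participant no benefit. No statistical result depends on it.

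**Working it through.** The plan gives no figure to reproduce beyond the 28-day window. The check has two parts.

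**1. Is a later test required anywhere?**

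| Section | Pregnancy test required after screening? |
|---|---|
| 2.2.2 Screening | No; this is the test itself, at any time from day -28 to dosing |
| 2.4 Baseline | No; not listed, and repeats within 28 days are waived |
| 3.2 Drug administration | No; EKG only |
| 3.4 Calendar, footnote 1 | No; screening only |
| 3.7.1 Removal criteria | No; acts on a positive result but schedules no test |
| 4 Concomitant measures | No; routine care is left free, with no test named |
| 16.2 Worksheet | No; PK tube only in the pre-dose row |

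The maximum test age at dosing is therefore 28 days. Under a 48-hour rule it would be 2 days, which is 26 days less.

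**2. How many exposures might this affect?**

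Inputs from the documents: a 28-day ceiling and at most 25 patients (section 3.1). Assumptions, none in the documents:

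- *n*, women of childbearing potential: 1 to 8
- *r*, annual pregnancy risk on contraception: 1% to 15%
- *L*, days from conception until a test can turn positive: 0 to 14

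A pregnancy is missed at dosing if conception falls within (test age + *L*) days before dosing. The window is 28 + *L* days now and 2 + *L* days with the fix, so the relative reduction in the window is 26 / (28 + *L*):

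- *L* = 0: 26/28 = 92.9%
- *L* = 7: 26/35 = 74.3%
- *L* = 10: 26/38 = 68.4%
- *L* = 14: 26/42 = 61.9%

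Expected undetected pregnancies over *d* days = *n* × [1 − (1 − *r*)^(*d*/365)]. The lower case is *n* = 1, *r* = 1%. The upper case is *n* = 8, *r* = 15%.

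| *L* (days) | Now (28 + *L*) | With fix (2 + *L*) | Difference |
|---|---|---|---|
| 0 | 0.00077 to 0.0991 | 0.00006 to 0.0071 | 0.00072 to 0.0920 |
| 10 | 0.00105 to 0.1342 | 0.00033 to 0.0426 | 0.00072 to 0.0916 |
| 14 | 0.00116 to 0.1482 | 0.00044 to 0.0568 | 0.00072 to 0.0914 |

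Example, upper case, *L* = 10: 8 × [1 − 0.85^(38/365)] = 0.1342 now and 8 × [1 − 0.85^(12/365)] = 0.0426 with the fix.

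The table assumes that every woman is tested exactly 28 days before dosing. With a shorter actual interval, upper case, *L* = 10, the difference is:

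- 14 days: 8 × [0.85^(12/365) − 0.85^(24/365)] = 0.0424
- 7 days: 8 × [0.85^(12/365) − 0.85^(17/365)] = 0.0177

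A middle case of 3 women, 5% annual risk and a 14-day interval gives about 0.005, or one exposure in about 200 such trials. The difference is zero if no woman of childbearing potential enrols, or if screening tests already fall within 48 hours of dosing.

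**The case against.** The strongest reply has four parts.

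- **The footnote.** It hangs on the laboratory row, which is marked at pre-treatment and at two post-dose visits, so its natural purpose is to exempt the pregnancy test from the post-dose panels. That reading is probably right. It does not close the gap, because the point rests on the absence of any later requirement, not on a prohibition.
- **Existing safeguards.** Contraception is mandatory, suspected pregnancy must be reported, and a positive test removes the patient. These narrow the case to an unsuspected pregnancy arising after a negative test, most plausibly from contraceptive failure. That limit is accepted. None of these measures detects such a pregnancy.
- **Routine preoperative care.** Section 4 says "Participation in this study will not limit any routine care", and the surgical team may well test. The documents neither require this nor tie it to the dosing decision. Since the infusion comes 2 to 4 hours before surgery, a surgical check not linked to dosing could come too late. The consent pages and the schema figure were not available, so the finding covers the available text only. A PK worksheet is also not where one would necessarily expect a pregnancy test, so its silence adds little on its own.
- **Size.** The upper estimate combines every unfavourable assumption, and the true lower bound is zero. Both statements are correct. They bear on the weight of the point, not on whether the gap exists.

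**Conclusion.** The point holds. The plan requires one pregnancy test, at screening, which may be up to 28 days old at the only dose, and nothing in the available text requires a nearer one. The 28-day figure is read directly from sections 2.2.2 and 3.4 and depends on no assumption.

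The expected benefit of a nearer test is small: about 0.0007 to 0.09 exposures prevented across the trial with a full 28-day gap and at least one woman of childbearing potential, at any detection lag from 0 to 14 days. It is at most about 0.04 or 0.02 if the usual interval is 14 or 7 days. The documents give no usual interval. The 26-day reduction is a reduction in test age, not in risk, because very early pregnancies would still be missed.

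The change is worth making because the exposure cannot be reversed, fetal effects are unknown, participants gain nothing directly and the remedy is cheap. It is an inexpensive safety improvement for an unlikely event and does not correct an error in the analysis.

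**What to change.** Keep the screening test for eligibility and replace the last sentence of footnote 1 in section 3.4 with:

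> For women of childbearing potential, a urine or serum beta-HCG is required within 48 hours before the LB100 infusion, and a negative result must be reviewed before dosing. A screening test or routine preoperative result inside that window suffices. No pregnancy test is required at the post-dose visits.

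The 48-hour limit is a judgement, not a derived safety threshold. It was chosen to match the window that section 5.1.1.1 already allows for the pre-dose blood sample.

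The cost is one inexpensive urine or blood test for each woman of childbearing potential whose screening result is older than 48 hours, plus the footnote wording. Patients are admitted for surgery, so an extra visit is unlikely, although the documents do not say how long before the infusion admission occurs. A patient who tests positive is not dosed, and enrolment can continue within the ceiling of 25.
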